6.7.1.2. TRABECTEDIN

Prior to re-treatment, patients must fulfil the baseline criteria defined previously (see Inclusion criteria section). If any of the following events occur at any time between cycles, the dose must be reduced to the lower level according to table below, for subsequent cycles:

- Neutropenia < 500/mm³ lasting for more than 5 days or associated with fever or infection
- Thrombocytopenia < 25,000/mm³
- Increase of bilirubin >ULN and/or AP >2.5 xULN
- Increase of AST or ALT > 5xULN which has not recovered by day 21
- Any other grade 3 or 4 adverse reactions (such as nausea, vomiting, fatigue)

For more information, please see trabectedin's SPC.

Once a dose has been reduced because of toxicity, dose escalation in the subsequent cycles is not allowed.

Dose level	Trabectedin dose (mg/m ²)
-1	0.8
1	1
2	1.2
3	1.5

Capillary Leak Syndrome cases (CLS) have been reported with trabectedin (frequency uncommon). If symptoms of possible CLS develop, such as unexplained edema with or without hypotension, reassess albumin level. A rapid decline in albumin level may be indicative of CLS. If a diagnosis of CLS is confirmed after exclusion of other causes, discontinue trabectedin and promptly initiate CLS treatment according to institutional guidelines.

Recommendation for management of LVEF results from baseline cardiac echography:

- Patients with a LVEF >50% and asymptomatic will be regularly clinically monitored for cardiac symptoms, and cardiac echography will be performed if clinically indicated.
- Patients with LVEF between 40% and <50% but asymptomatic will be regularly clinically monitored for cardiac symptoms, and cardiac echography will be performed at 6 weeks and 12 weeks and every 12 weeks thereafter.
- Patients with LVEF <40% or with clinically symptomatic cardiac dysfunction (any % of LVEF at baseline) **will be excluded** from the trial and specialised cardiac management will be advised.

Recommendation for dose adaptation in case of LVEF drop during treatment with trabectedin :

- For patients with Grade 3 or 4 cardiac adverse events indicative of cardiomyopathy or for patients with a LVEF that decreases below the LLN (assessed as either an absolute decrease of LVEF of $\geq 15\%$ or <LLN with an absolute decrease of $\geq 5\%$), trabectedin should be discontinued.
- In case of cardiac symptoms, no matter the LVEF, trabectedin will be stopped and specialised cardiac management will be advised.

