10.6. Report of Hepatic function abnormality

Hepatic function abnormality (as defined by cases where a subject shows an AST or ALT $\geq 3 \times \text{ULN}$ and total bilirubin $\geq 2 \times \text{ULN}$ in a study subject, with or without associated clinical manifestations, is required to be reported as "hepatic function abnormal" within 24 hours of knowledge of the event to the sponsor using the SAE form unless a definitive underlying diagnosis for the abnormality (e.g., cholelithiasis or bile duct obstruction) that is unrelated to investigational product has been confirmed.

Hy's Law: Cases where a patient shows elevations in liver biochemistry may require further evaluation and occurrences of AST or ALT $\geq 3 \times \text{ULN}$ together with total bilirubin $\geq 2 \times \text{ULN}$ may need to be reported as SAEs. Please refer to Appendix 4, the Toxicity Management Guidelines, for further instruction on cases of increases in liver biochemistry and evaluation of Hy's law.

- If the definitive underlying diagnosis for the abnormality has been established and is unrelated to investigational product, the decision to continue dosing of the study subject will be based on the clinical judgment of the investigator.
- If no definitive underlying diagnosis for the abnormality is established, dosing of the study subject must be interrupted immediately. Follow-up investigations and inquiries must be initiated by the investigational site without delay.

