	Grade 2	Hold Study drug/study regimen dose until resolution to Grade ≤ 1 
 If toxicity worsens, then treat as Grade 3 or grade 4. If toxicity improves to Grade ≤ 1 or baseline and there were no elevations in bilirubine, resume study drug / study regimen after completion of steroid taper (<10 mg prednisone or equivalent). Permanently discontinue study drug/study regimen for any case meeting Hy's law criteria (AST and/or ALT $>3 \times$ ULN + bilirubin $>2 \times$ ULN without initial findings of cholestasis (i.e., elevated ALP) and in the absence of any alternative cause	
 Regular and frequent checking of LFTs (e.g., every 1 to 2 days) until LFT elevations improve or resolve. If no resolution to \leqGrade 1 in 1 to 2 days, consider, as necessary, discussing with Clinical Study Lead. If event is persistent (>2 to 3 days) or worsens, promptly start prednisone 1 to 2 mg/kg/day PO or IV equivalent. Restart once resolved to Grade ≤ 1 WITH DOSE REDUCTION FOR TRABECTEDIN Keep checking transaminitis twice weekly for the next cycle
	Grade 3:	
 Hold study drug/study regimen For elevations in transaminases $\leq 8 \times$ ULN (and no elevations in bilirubin), or elevations in bilirubin $\leq 5 \times$ ULN until resolution to Grade <1 or baseline Permanently discontinue study drug/study regimen for elevations in transaminases $>8 \times$ ULN or any elevations in bilirubin $>5 \times$ ULN 	For Grade 3 or 4 
 Promptly initiate empiric IV methylprednisolone at 1 to 2 mg/kg/day or equivalent. If still no improvement within 2 to 3 days despite 1 to 2 mg/kg/day methylprednisolone IV or equivalent, promptly start treatment with an immunosuppressant therapy (i.e., mycophenolate mofetil 0.5-1 g every 12 hours then taper in consultation with hepatology consult or relevant practice guidelines). Discuss with Clinical Study Lead if mycophenolate is not available. Infliximab should NOT be used. Perform Hepatology consult, abdominal workup and imaging as appropriate.

Adverse Events	Severity Grade of the Event (NCI CTCAE version 4.03)	Dose Modifications	Toxicity Management
		
 - Dose modification for Trabectedin is mandatory if grade 3 If No decreasing of Transaminitis kinetic within the 4th week after previous infusion, permanently discontinue entire study regimen 	
	Grade 4	Permanently discontinue study drug/study	

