Grade 3 or 4	
For Grade 3 or 4: Permanently discontinue study drug/study regimen
	
For Grade 3 or 4:
 
 - Manage severe infusion-related reactions per institutional standards appropriate clinical practice guidelines, and society guidelines (e.g., IM epinephrine, followed by IV diphenhydramine and famotidine, and IV glucocorticoid)

Non-immune Mediated Reactions		
Severity Grade of the Event (NCI CTCAE version 4.03)	Dose Modification	Toxicity Management
Any Grade	Note: dose modifications are not required for adverse events not deemed to be related to study treatment (i.e. events due to underlying disease) or for laboratory abnormalities not deemed to be clinically significant.	Treat accordingly, as per institutional standard
Grade 1	No dose modifications	Treat accordingly, as per institutional standard
Grade 2	Hold study drug/study regimen until resolution to \leq Grade 1 or baseline	Treat accordingly, as per institutional standard
Grade 3	Hold study drug/study regimen until resolution to \leq Grade 1 or baseline For AEs that downgrade to \leq Grade 2 within 7 days or resolve to \leq Grade 1 or baseline within 14 days, resume study drug/study regimen administration. Otherwise, discontinue study drug/study regimen	Treat accordingly, as per institutional standard
Grade 4	Discontinue Study drug/study regimen (Note for Grade 4 labs, decision to discontinue would be based on accompanying clinical signs/symptoms, the Investigator's clinical judgment and consultation with the Sponsor)	Treat accordingly, as per institutional standard

^a ASCO Educational Book 2015 "Managing Immune Checkpoint Blocking Antibody Side Effects" by Michael Postow MD.

^b FDA Liver Guidance Document 2009 Guidance for Industry: Drug Induced Liver Injury – Premarketing Clinical Evaluation.

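### For clinical grade 4 and late-recovering grade 3 non-immune events, Section 6.7.1.2 and Appendix 4 are not reconciled for trabectedin, and restart after a Hy's-law case is left open

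*Protocol*

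**What the plan says.** **Section 6.7.1.2 (trabectedin).** It opens with a condition: "Prior to re-treatment, patients must fulfil the baseline criteria defined previously (see Inclusion criteria section"). It then lists events after which "the dose must be reduced to the lower level according to table below, for subsequent cycles". The list includes "Any other grade 3 or 4 adverse reactions (such as nausea, vomiting, fatigue") and "Increase of bilirubin >ULN and/or AP >2.5 xULN". It sets no time limit for recovery and does not provide for discontinuation after these events. Section 6.7 likewise says that doses in the expansion cohorts are reduced for haematological and other adverse events.

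**Appendix 4, non-immune table.** Grade 4: "Discontinue Study drug/study regimen (Note for Grade 4 labs" are left to clinical signs, investigator judgement and consultation with the sponsor). Grade 3: hold until grade 1 or less or baseline; resume if the event falls to grade 2 or less within 7 days, or to grade 1 or less or baseline within 14 days. "Otherwise, discontinue study drug/study regimen".

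**Hy's law.** For AST or ALT at least 3x ULN with bilirubin at least 2x ULN, Section 10.6 says: "If no definitive underlying diagnosis for the abnormality is established, dosing of the study subject must be interrupted immediately". It refers the reader to Appendix 4 for further instruction. The grade 2 hepatitis row of Appendix 4 says: "Permanently discontinue study drug/study regimen for any case meeting Hy's law criteria", meaning above 3x and above 2x ULN, without initial cholestasis and without an alternative cause.

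**The concern.** A patient with a severe non-immune event may stay on reduced trabectedin under one text and leave the regimen under the other, and no passage says which prevails. Safety comes first: an investigator holding this protocol has two instructions for the same event.

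There is a statistical side as well. The primary response endpoint of the expansion cohorts is recorded from treatment start to end of treatment (Section 8.1), and responses need confirmation at least 4 weeks later. The RP2D draws on safety data from all patients (Section 3.4). If the rule for leaving treatment depends on which section is followed, then exposure, time at risk of being counted a responder, and cumulative toxicity depend on it too.

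**Working it through.** The plan states no figure to reproduce. The check is a comparison of the rules by event class.

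| Event | Section 6.7.1.2 (trabectedin) | Appendix 4 or Section 10.6 | Result |
|---|---|---|---|
| Clinical grade 4, non-immune | Reduce in later cycles after baseline criteria are met | Discontinue | Conflict, if the term covers trabectedin |
| Laboratory grade 4, non-immune | Reduce if listed | Discretionary | No fixed conflict |
| Grade 3, recovers within 7/14 days | Wait for baseline criteria, then reduce | Hold, then resume | Broadly compatible |
| Grade 3, misses both limits | Wait (no limit), then reduce | Discontinue | Conflict, if the term covers trabectedin |
| Hy's-law pattern, 10.6 against Appendix 4 | – | Interrupt and investigate; then discontinue permanently if no alternative cause | Successive steps |
| Hy's-law case, 6.7.1.2 against Appendix 4 | Bilirubin line: reduce in later cycles, no exception | Discontinue permanently | Unreconciled for trabectedin |

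**Illustration (assumed course).** Fatigue is grade 3 at day 7, grade 2 at day 14 and grade 1 at day 21. It misses the 7-day limit (still grade 3) and the 14-day limit (not yet grade 1), so Appendix 4 discontinues. Under 6.7.1.2 the patient can meet the baseline criteria again at day 21 and restart trabectedin one level lower.

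**The grade 3 row on its own terms.** Take an event that reaches grade 2 on day 6. The first sentence keeps the patient on hold, because grade 1 or baseline has not been reached. The second resumes dosing, because grade 2 was reached within 7 days. Both cannot be followed.

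**Scope of the term.** The evidence points both ways.
- Durvalumab only: the appendix title; Section 6.7.1.1, which sends durvalumab to Appendix 4, while 6.7.1.2 gives trabectedin its own list; and the column heading of the other-immune table, which names durvalumab.
- Both drugs: the hepatitis rows, which make trabectedin dose modification mandatory at grade 3, require a reduced trabectedin dose on restart after grade 2, and in one case stop the entire regimen; and the non-immune table, whose column heading names no drug.

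**Hy's-law triggers.** At least 3x/2x ULN (10.6) and above 3x/2x ULN (Appendix 4) differ numerically only at exact equality. The requirement of no initial cholestasis is the larger difference.

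**Scale.** Each cohort needs 14 eligible and assessable patients, so one patient is 1/14 = 7.1 percentage points. The cohort is declared worthy of further testing on one response. At the design rate of 20%, P(exactly one responder) = 14 x 0.2 x 0.8^13 = 14 x 0.2 x 0.0550 = 15.4%. In such a cohort the conclusion rests on one patient. This shows only how little the decision rule rests on: the conclusion would change only if that patient had an affected event and was stopped before the response appeared or could be confirmed. Section 4.4 also counts patients as on treatment until 30 days after the last dose (unless a new antitumour therapy starts), and Section 4.8 schedules a tumour assessment at about that time, so some responses could still be confirmed after stopping.

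The nausea, fatigue and vomiting rates in Section 1.3.3 (64.7%, 58.3%, 40.1%) are for trabectedin alone and are not restricted to grade 3-4. They do not give the share affected.

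**The case against.** The strongest reply is that the rules are split by drug. On that reading Appendix 4 governs durvalumab, 6.7.1.2 governs trabectedin, and both apply at once: trabectedin reduced, durvalumab stopped. Section 6.7.2 shows that stopping durvalumab alone is contemplated. Appendix 4 also calls itself a recommendation for immune-mediated events. This reading is tenable, but the documents do not establish it. The same appendix directs trabectedin dosing in its hepatitis rows, and no passage says that trabectedin continues alone after a non-immune discontinuation. A clarification is needed on either reading.

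Other parts of the reply stand, and they limit the point. A reader might infer that body and appendix give opposite orders for all grade 3-4 toxicity and for Hy's law. The documents do not support that:
- Grade 3 events that recover in time are held and then resumed under both texts.
- Grade 4 laboratory events are discretionary in Appendix 4.
- Section 10.6 interrupts pending work-up and refers to Appendix 4, so interruption and permanent discontinuation follow one another.
- Section 6.7.1.2 does not simply reduce and continue. The baseline criteria include bilirubin at or below ULN and AST/ALT at or below 2.5x ULN (Section 4.1), so a Hy's-law patient cannot be re-dosed before recovery.
- Section 4.4 stops treatment for any adverse event that, in the opinion of the investigator or sponsor, contraindicates further dosing.

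Divergence between sites is a possibility, not a finding. In the escalation part, toxicities that would lead to dose modification are discussed with the sponsor (Section 6.7). The MTD rests on the first 21 days, before any reduction in later cycles.

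**Conclusion.** The point holds in limited form. Two classes of non-immune event are unreconciled for trabectedin: clinical grade 4 events, and grade 3 events that miss the Appendix 4 limits. This rests on *study drug/study regimen* including trabectedin; if it does not, the defect is that the text never says so. Two further faults do not depend on that assumption in the same way. The grade 3 row contradicts itself whichever drug it governs. And because the bilirubin line in 6.7.1.2 has no Hy's-law exception or cross-reference, the text does not settle whether trabectedin may restart after recovery.

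The effect on response, exposure or the RP2D data cannot be quantified from the documents, because the frequency of the affected events is not given. The 7.1 points and 15.4% describe how small the cohorts are, not an expected bias. The point should still be corrected, because it concerns stop-or-continue instructions for severe toxicity. No view is taken here on which clinical rule is right.

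**What to change.** By amendment:
1. Reconcile Section 6.7.1.2 with the non-immune and hepatitis tables of Appendix 4 so that each event class has one instruction, stated separately for trabectedin and durvalumab.
2. Define whether *study drug/study regimen* includes trabectedin, and say which text prevails if the two differ.
3. Remove the hold/resume contradiction in the grade 3 non-immune row.
4. Cross-reference Hy's law in 6.7.1.2, state what happens to trabectedin after recovery, and align the triggers in Section 10.6 and Appendix 4.

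The sponsor's clinicians choose the content of each instruction. The cost is amendment wording and a memo to the sites; sample size and analysis methods do not change. SAP Table 4.3 already reports reductions, delays and discontinuations with reasons. Reporting these by drug would show how patients treated before the amendment were managed.

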6.7.2. Events of clinical interest and immune mediated adverse event (imeics)

Events of clinical interest of a potential immunologic etiology (imECIs) may be defined as an adverse event of unknown etiology, associated with drug exposure and is consistent with an immune phenomenon. imAEs may be predicted based on the nature of the durvalumab compound, its mechanism of action, and reported experience with immunotherapies that have a similar mechanism of action. Special attention should be paid to AEs that may be suggestive of potential imAEs. An imAE can occur shortly after the first dose or several months after the last dose of treatment.

If an imAE is suspected, efforts should be made to rule out neoplastic, infectious, metabolic, toxin or other etiologic causes prior to labeling an adverse event as an imAE.

All imAE should be reported to sponsor (see section 11.7).

imAE will be managed according to the toxicity management guidelines (appendix 4). Durvalumab will be delayed until if the adverse reaction remains at Grade 1 or less.

If another episode of a severe adverse reaction occurs, only Durvalumab will be permanently discontinued.

Patient requiring 2 delays of Durvalumab injection should go off protocol therapy.

Ir-AE are described in this section, but not limited to the items outlined below. For management, refer to the appendix 4 and to most updated Investigator Brochure.

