6.7. Dosing delays/dose modifications and adverse event management

No changes in durvalumab dose are allowed. If immune related adverse events occur, the durvalumab administration will be adjusted (delayed doses) as per the toxicity management guidelines (Appendix 4).

Dose escalation: Toxicities that would lead to dose modification should be discussed with the sponsor.

Expansion cohorts: Doses will be reduced for haematological and other adverse events. Dose adjustments are to be made according to the greatest degree of toxicity. Adverse events will be graded using the NCI Common Terminology Criteria for Adverse Events Version 4.03 (NI-CTCAE).

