6.7.1. General rules for dose modification

6.7.1.1. DURVALUMAB

Management of toxicity is described in appendix 4.

Reactions may occur during or after the infusion of study medication. The reaction may cause fever or chills and a change in blood pressure or difficulty in breathing.

In the event of a \leq Grade 2 infusion-related reaction, the infusion rate of study drug may be decreased by 50% or interrupted until resolution of the event (up to 4 hours) and re-initiated at 50% of the initial rate until completion of the infusion. For subjects with a \leq Grade 2 infusion-related reaction, subsequent infusions may be administered at 50% of the initial rate. Acetaminophen and/or an antihistamine (e.g., diphenhydramine) or equivalent medications per institutional standard may be administered at the discretion of the investigator.

If the infusion-related reaction is Grade 3 or higher in severity, study drug will be discontinued.

The standard infusion time is one hour, however if there are interruptions during infusion, the total allowed time from infusion start to completion of infusion should not exceed 4 hours at room temperature, with maximum total time at room temperature not exceeding 4 hours (otherwise requires new infusion preparation).

As with any antibody, allergic reactions to dose administration are possible. Appropriate drugs and medical equipment to treat acute anaphylactic reactions must be immediately available, and study personnel must be trained to recognize and treat anaphylaxis. The study site must have immediate access to emergency resuscitation teams and equipment in addition to the ability to admit subjects to an intensive care unit if necessary.

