Patients with a global deterioration of health status requiring discontinuation of treatment without objective evidence of disease progression at that time should be reported as 'symptomatic deterioration'. Every effort should be made to document objective progression even after discontinuation of treatment. Symptomatic deterioration is *not* a descriptor of an objective response: it is a reason for stopping study therapy. The objective response status of such patients is to be determined by evaluation of target and non-target disease as shown in Tables belows.

APPENDIX 4: DOSING MODIFICATION AND TOXICITY MANAGEMENT GUIDELINES FOR IMMUNE-MEDIATED, INFUSION RELATED, AND NON IMMUNE-MEDIATED REACTIONS FOR DURVALUMAB

General Considerations Regarding Immune-Mediated Reactions

These guidelines are provided as a recommendation to support investigators in the management of potential immune-mediated adverse events (imAEs).

Immune-mediated events can occur in nearly any organ or tissue, therefore, these guidelines may not include all the possible immune-mediated reactions. Investigators are advised to take into consideration the appropriate practice guidelines and other society guidelines (e.g., National Comprehensive Cancer Network (NCCN), European Society of Medical Oncology (ESMO)) in the management of these events. Refer to the section of the table titled "Other -Immune-Mediated Reactions" for general guidance on imAEs not noted in the "Specific Immune-Mediated Reactions" section.

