	Grade 2	Hold study drug/study regimen until resolution to Grade ≤ 1 or baseline 
 • If toxicity worsens then treat as Grade 3 or Grade 4 • If toxicity improves to Grade ≤ 1 or baseline then resume study drug/study regimen after completion of steroid taper 	
For Grade 2:
 
 - Consider symptomatic treatment including hydration, electrolyte replacement, diuretics, - Carefully monitor serum creatinine every 2 to 3 days and as clinically warranted - Consult Nephrologist and consider renal biopsy if clinically indicated - If event is persistent beyond 3 to 5 days or worsens, promptly start prednisone 1 to 2 mg/kg/day PO or IV equivalent - If event is not responsive within 3 to 5 days or worsens despite prednisone at 1 to 2 mg/kg/day PO or IV equivalent, consider additional workup - When event returns to baseline, resume study drug/study regimen and routine serum creatinine monitoring per study protocol
	Grade 3 or 4	Permanently discontinue study drug/study regimen	
For Grade 3 or 4:
 
 - Carefully monitor serum creatinine - Consult Nephrologist and consider renal biopsy if clinically indicated - Promptly start prednisone 1 to 2 mg/kg/day PO or IV equivalent - If event is not responsive within 3 to 5 days or worsens despite prednisone at 1 to 2 mg/kg/day PO or IV equivalent, consider additional workup and prompt treatment with an immunosuppressant in consultation with a nephrologist
Adverse Events	Severity Grade of the Event (NCI CTCAE version 4.03)	Dose Modifications	Toxicity Management
Rash or dermatitis (including)	Any Grade (refer to NCI CTCAE v 5 for definition of severity/grade depending on type of skin)	General Guidance	
For Any Grade:
 
 - Monitor for signs and symptoms of dermatitis (rash and pruritus) - HOLD STUDY DRUG IF STEVENS-JOHNSON SYNDROME (SJS), TOXIC EPIDERMAL NECROLYSIS (TEN), OR OTHER SEVERE CUTANEOUS ADVERSE REACTION (SCAR) IS SUSPECTED.

Pemphigoid	rash)		
 - PERMANENTLY DISCONTINUE STUDY DRUG IF SJS, TEN, OR SCAR IS CONFIRMED.
	Grade 1	No dose modification	
For Grade 1:
 
 - Consider symptomatic treatment including oral antipruritics (e.g., diphenhydramine or hydroxyzine) and topical therapy (e.g., emollient, lotion, or institutional standard)

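### Section 6.7.2 sets its own delay, stop and off-therapy rules for immune-mediated events beside Appendix 4 and does not say which prevails where the two differ

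*Protocol*

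**What the plan says.** Protocol 6.7.1.1 states: "Management of toxicity is described in appendix 4". Section 6.7 refers durvalumab delays for immune events to the same appendix, and 6.7.2 repeats the pointer: "imAE will be managed according to the toxicity management guidelines (appendix 4". Section 6.7.2 then gives three rules that are not tied to any event type:

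- Delay: "Durvalumab will be delayed until if the adverse reaction remains at Grade 1 or less".
- Recurrence: "If another episode of a severe adverse reaction occurs, only Durvalumab will be permanently discontinued".
- Leaving therapy: "Patient requiring 2 delays of Durvalumab injection should go off protocol therapy".

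It closes by referring again to Appendix 4 and to the Investigator's Brochure. Nothing in 6.7, 6.7.1.1, 6.7.2 or Appendix 4 gives an order of precedence.

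Appendix 4 opens by describing its own status: "These guidelines are provided as a recommendation to support investigators in the management of potential immune-mediated adverse events (imAEs". Its dosing orders are set out by event and grade. At grade 3 or 4 nephritis, for example, the order is "Permanently discontinue study drug/study regimen".

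**The concern.** These are orders about giving more drug after severe immune toxicity. The body text uses *will* and *should*, while the appendix calls itself a recommendation. An investigator who follows the body text where the two differ could delay and resume durvalumab after an event for which the appendix ends it. The same reading could withhold durvalumab from a patient the appendix would keep on it, or continue trabectedin in a hepatitis case for which the appendix ends both drugs.

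The two-delay rule adds uncertainty of its own, because sites may count delays differently and so remove comparable patients at different times. That has some bearing on the analysis. The RP2D rests on safety data from all patients (protocol 3.2). Objective response in the expansion cohorts is recorded only until the end of treatment (8.1). SAP Table 4.3 reports counts of delays and discontinuations. The size of any such effect cannot be derived from the documents.

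**Working it through.** The plan gives no figure on this point. The check is a comparison of texts, followed by two small calculations.

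**1. Side by side.** The delay sentence is taken in its most natural repair: hold durvalumab until the event is grade 1 or less.

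| Case | 6.7.2 read alone | Appendix 4 |
|---|---|---|
| First grade 3 nephritis, acute pancreatitis or neurotoxicity | Delay; stop at another severe episode | Permanent stop now |
| Hepatitis, transaminases above 8 x ULN or bilirubin above 5 x ULN | Delay; at another severe episode stop durvalumab only | Permanent stop of study drug/study regimen |
| Grade 3 hepatitis, transaminases not falling by the fourth week after infusion | As above | Permanent stop of the entire regimen |
| Isolated hypothyroidism, grade 2 to 4 row | Delay while above grade 1 | Replacement therapy, no interruption |
| Isolated amylase/lipase rise, grade 2 to 4 | Delay while above grade 1 | Consider continuing, with specialist advice, if no evidence of pancreatitis |
| Number of delays allowed | Two, then off protocol therapy | No such limit |

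**2. How many event blocks.** Leaving out the guidance meant only for hepatocellular carcinoma, Appendix 4 has 12 event-specific blocks: pneumonitis, colitis, hepatitis, nephritis, rash, endocrinopathy, amylase/lipase, pancreatitis, neurotoxicity, peripheral neuromotor syndromes, myocarditis and myositis.

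- Five order an unconditional permanent stop at a first grade 3 event: pneumonitis, nephritis, pancreatitis, neurotoxicity and myocarditis.
- Pneumonitis and myocarditis are largely handled in the body text (6.7.2.1 and 6.7.2.7). That leaves 5 − 2 = 3. Section 6.7.2.4 only describes nephritis, and pancreatitis and neurotoxicity have no subsection.
- Eight require a completed steroid taper before restart: pneumonitis, colitis, hepatitis, nephritis, rash, endocrinopathy, pancreatitis and myocarditis. Section 6.7.2 does not mention the taper. This is an omission, not an opposite order.

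**3. What a delay is.** The general text of Appendix 4 allows up to 12 weeks to bring steroids down to 10 mg prednisone or less. At 21-day cycles, 12 × 7 / 21 = 84 / 21 = 4 injections. If each missed injection is a delay, a patient on such a course leaves protocol therapy at the second. If one continuous hold is one delay, the same patient stays.

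**4. How often the first-episode conflict could arise.** Protocol 1.4.3 lists the treatment-related events of grade 3 or higher reported in 3 or more of 694 monotherapy subjects. Nephritis, pancreatitis and neurotoxicity are not listed, so each had at most 2.

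- Per term: at most 2/694 = 0.29%.
- Three terms, 20 + 30 = 50 patients: at most 50 × 6/694 = 0.43 expected events.
- Chance of at least one: at most 1 − (1 − 6/694)^50 = 0.35.

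The range is therefore 0 to 0.43 events and 0 to 35%. It assumes one adverse-event term per event type and that the monotherapy rate carries over; the documents give no rate for the combination. Hepatitis, thyroid and enzyme events are not covered by this figure.

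**The case against.** The strongest reply is that there is no conflict. Sections 6.7, 6.7.1.1 and 6.7.2 all send the investigator to Appendix 4, and the *will* in 6.7.2 makes it binding despite its generic label. The second-episode sentence matters only where treatment has resumed, so an appendix stop at the first episode means it never comes into play. Divergence is also limited in practice: there are three centres, toxicities leading to dose modification in escalation are to be discussed with the sponsor (6.7), and dose reductions or interruptions outside protocol procedures are to be discussed with the coordinator first (10.8).

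Much of this stands, and it is why the point is modest. But a cross-reference does not settle precedence when the referring section goes on to give different rules. Nor does it repair the delay sentence, define a delay, or reconcile stopping only durvalumab with an appendix row that can end both drugs.

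Three stronger readings are tempting and should be resisted.

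- *Appendix 4 is looser on recurrence.* Five grade 3 rows (colitis, hepatitis up to 8 x ULN, rash, peripheral neuromotor syndromes, myositis) allow hold and resume with no recurrence stop in the row. The appendix's general text, however, permanently stops treatment for recurrent grade 3 events that need systemic immunosuppression. Four of the five rows order IV methylprednisolone at grade 3, and exclusion criterion 2 counts glucocorticoids as immunosuppressive. Only peripheral neuromotor syndromes lack a uniform steroid order.
- *Study drug/study regimen simply means durvalumab.* The grade 2 hepatitis row holds study drug/study regimen and restarts with a trabectedin dose reduction, so that hold evidently covers trabectedin.
- *The trabectedin re-treatment rule (6.7.1.2 with inclusion criterion 12f) contradicts the hypothyroidism row.* If that row concerns durvalumab, it says nothing about trabectedin. The documents do not establish a contradiction.

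**Conclusion.** The point holds as a modest safety-consistency correction that should be made. Section 6.7.2 contains a sentence that cannot be followed as written, an undefined term that decides who leaves therapy, and general rules that, read literally, differ from Appendix 4. The differences concern first grade 3 stops in 3 of 12 event blocks, the scope of stopping in hepatitis, and two situations in which the appendix lets dosing continue.

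A reader might infer that severe immune toxicity is left unmanaged. The documents do not support that: detailed orders exist, and the pointers make them the likely intended source. The first-episode events should be rare, at most 0.43 expected in 50 patients under the stated assumptions. The 35% is an upper limit on any such event occurring, not on sites dosing differently. It could be higher if neurotoxicity, which spans several conditions, was reported under several terms, or if the combination is more toxic than monotherapy.

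**What to change.** Make one amendment to section 6.7.

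1. Rewrite the delay sentence so that durvalumab is held and resumed as the Appendix 4 event row states, including any steroid taper it requires. State that the event rows govern, including the first-episode grade 3 stops and the rows that allow dosing without interruption. State that the recurrent-severe stop in 6.7.2 and the recurrent grade 2 pneumonitis stop in 6.7.2.1 apply in addition.
2. For the two-delay rule, define one continuous hold as one delay.
3. State that stopping only durvalumab does not override the hepatitis row. Its holds and its permanent stops (Hy's law, transaminases above 8 x ULN, bilirubin above 5 x ULN, transaminases not falling by the fourth week, grade 4) apply to both drugs.

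Do not add a blanket rule that study drug/study regimen means durvalumab only. It would turn the hepatitis stops into durvalumab-only stops and leave trabectedin, whose hepatotoxicity is noted in 6.6.4.2, to restart at a reduced dose under 6.7.1.2. Do not relax criterion 12f.

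The amendment needs no extra visits, patients, data fields or analyses. Its downside is that a few patients will stop durvalumab, or both drugs, earlier than 6.7.2 read alone would require.
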